3.3.4 Incremental effects of volanesorsen on lipid measures

The incremental effects of volanesorsen on fasting TG and other fasting lipid measurements will be explored and the association between percent changes in fasting lipid measurements and total amount of drug received will be examined. Scatter plots of percent change from baseline in fasting lipid measurements including TG, non-HDL-C, apoB, HDL-C, apoA-1, VLDL-C, LDL-C, total cholesterol, and total apoC-III versus total amount of volanesorsen received and corresponding Pearson's correlation coefficient will be presented. For patients treated with volanesorsen in index studies, the **Index Study Baseline** will be used, and for patients treated with placebo in index studies and Group 3 patients, the **Open-label Study Baseline** will be used. The total amount of doses will be the total number of injections (volanesorsen) received from both index studies and open-label study regardless if full dosing is administered or not.

All patients will be presented in the same graph no matter if the patient is from the index studies or the open-label study.

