2.2 Randomization & Treatment Allocation

This is an open-label study to the Phase 3 study of rolled over volanesorsen patients with FCS (ISIS 304801-CS6 or ISIS 304801-CS16) and newly-enrolled patients who did not participate in the index studies. All patients will initiate treatment with volanesorsen 300mg by SC injection weekly and continue on this dose and regimen unless they meet a per-protocol dose adjustment criterion.

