Summary figures will be generated for platelet counts over time (absolute values, absolute change from baseline, and percent change from baseline) in patients treated with placebo in ISIS 304801-CS6 who then treated with Volanesorsen in ISIS 304801-CS7.

A summary figure will be generated for platelet counts over time (mean and SEM of absolute values) for treatment naïve patients. The first event of platelet count < 50,000/mm³ will be annotated in the figure. This figure will also be generated by weight group (<70kg; >=70kg).

A scatter plot will be generated for nadir platelet counts during on-treatment period vs. selected factors:

Body Weight (kg)
BMI
The Total Number of Injections
Baseline Spleen Volume (mL)
Baseline Fasting Triglycerides (mmol/L)
Baseline Fasting Apolipoprotein CIII (g/L)

The incidence of patients with post-baseline lab results falling in each of the following categories will be summarized for the safety set:

- Any serum creatinine >=0.3 mg/dL higher than baseline
- Any serum creatinine >=50% higher than baseline
- Final visit serum creatinine >=0.3 mg/dL higher than baseline
- Final visit serum creatinine >=50% higher than baseline

Summary of selected hematology assessment (white blood cell count, neutrophil, hemoglobin, and hematocrit) over time will be generated. Summary of selected urinalysis assessment (urinary protein, and urinary albumin), and normalized urine albumin and protein to creatinine (urine albumin/creatinine ratio, urine protein/creatinine ratio) over time will be generated. Corresponding summary figures will be generated as well. Urine albumin/creatinine ratio will be calculated as 1000 * urine albumin (mg/dL) / urine creatinine (mg/dL),

Shift tables of on-study urine albumin/creatinine ratio and urine protein/creatinine ratio will be generated with below ranges:

Urine Albumin/creatinine ratio	Urine Protein/creatinine ratio
< 30 mg/g	< 150 mg/g
30 to < 300 mg/g	150 to < 500 mg/g
>= 300 mg/g	500 to < 1000 mg/g
	>= 1000 mg/g

A listing for patients with ALT or AST > 3 x ULN will be generated to present all ALT, AST, Bilirubin, and ALP records from central and local lab.

A listing will be provided for patients who terminated treatment due to a protocol-defined stopping rule (see Protocol section 8.6 for details) with categories (liver chemistry elevation, renal function test results, platelet count results) and narratives.

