3.5.5 Exposure

Treatment duration in days, number of injections of Study Drug, compliance to Study Drug, dose adjustment and dose interruption/pauses will be summarized for the safety set.

- Treatment duration in days is defined as the last day on Study Drug minus the first day on Study Drug plus one. This will be derived for both index study period and the open-label study period.
- Number of injections of Study Drug received includes those for which full volume of dose was not given.
- Number of injections of Study Drug received for patients on active treatment in the index study will be the number of injections of Study Drug received from the first dose of the index study. Number of injections of Study Drug received for patients on placebo in the index study will be from the first dose of the open-label study.

Treatment duration in months during index study and open-label study will be summarized for the safety set.

- >=3 month category is defined as treatment duration in days >=85 days
- >=6 month category is defined as treatment duration in days >=176 days
- >=9 month category is defined as treatment duration in days >=267 days
- >=12 month category is defined as treatment duration in days >=358 days
- >=18 month category is defined as treatment duration in days >=541 days
- >=24 month category is defined as treatment duration in days >=723 days

Compliance to Study Drug will be summarized by descriptive statistics.

- Compliance of the open-label study for Group 1, Group 2 and Group 3 will be calculated as follows:
$$100 \times (\text{number of injections of Study Drug in the open-label study}) / (\text{number of injections scheduled during the Open-label Study Treatment Period})$$

- Compliance of the index study (ISIS 304801-CS6 or ISIS 304801-CS16) and open-label study overall for Group 1 and Group 2 will be calculated as follows:

$$\frac{100 \times (\text{number of injections of Study Drug in the index study (ISIS 304801-CS6 or ISIS 304801-CS16)} + \text{number of injections of Study Drug in the open-label study})}{(\text{number of injections scheduled during the treatment period in the index study (ISIS 304801-CS6 or ISIS 304801-CS16)} + \text{number of injections scheduled during the treatment period in the open-label study})}$$

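### Section 3.3.4 sets lipid change against an uncapped count of injections, so the pooled correlation largely reflects time on treatment and prior study rather than amount of drug

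*SAP*

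**What the plan says.** SAP Section 3.3.4 gives its aim as follows: "the association between percent changes in fasting lipid measurements and total amount of drug received will be examined". It plans scatter plots for nine lipid measures and adds that the "corresponding Pearson's correlation coefficient will be presented". The exposure variable is the "total number of injections (volanesorsen) received from both index studies and open-label study regardless if full dosing is administered or not". Patients who had volanesorsen in an index study are measured from the index baseline, and everyone else from the open-label baseline. All are pooled: "All patients will be presented in the same graph no matter if the patient is from the index studies or the open-label study". The section names no lipid time point and does not say when counting of injections ends.

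Three other places bear on the count:

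- Section 3.5.5 counts part doses in the same way: "Number of injections of Study Drug received includes those for which full volume of dose was not given".
- Section 2.2 has patients start at 300 mg weekly and "continue on this dose and regimen unless they meet a per-protocol dose adjustment criterion".
- Section 2.1.2 allows a biweekly schedule for safety reasons.

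The same count appears once more, in Section 3.5.4.2: "A scatter plot will be generated for nadir platelet counts during on-treatment period vs. selected factors". One of the six factors listed there is "The Total Number of Injections". No correlation and no dose-related aim is stated for that plot.

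**The concern.** A count of all injections departs from the amount of drug behind a lipid value in three ways.

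- **Amount.** A reduced or incomplete injection counts the same as a full one.
- **Timing.** Injections given after the lipid sample cannot have influenced it, yet they move the patient along the axis.
- **Group.** Patients previously on volanesorsen carry 6 or 12 months of index-study injections and a different baseline, so position on the axis partly encodes the study of origin.

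Total injections also depend on whether a patient stays on treatment, and that may depend on response and tolerability. A correlation could then appear with no dose effect behind it, and be reported as evidence of an incremental effect of the drug.

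**Working it through.** The SAP gives no figure for this point, so there is none to reproduce. Two checks follow. The first uses SAP inputs with full weekly dosing assumed. The second rests on assumed inputs.

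**1. Share of plotted injections given after the lipid value**

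Inputs:

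- Weekly dosing from Day 1, 52 weeks plus up to 52 more (Sections 1.1 and 2.1.3), so open-label totals T = 52 or 104.
- Samples drawn before the day's dose (Section 2.1.2).
- Later day of each lipid endpoint: Day 85, 176 or 358 (Section 3.3.2).
- Prior active treatment of 12 months in CS6 and 6 months in CS16 (Section 3.4.1.2), taken as p = 52 and p = 26 weekly injections; p = 0 for treatment-naive patients.

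Open-label injections before a sample on day d are b = (d − 1)/7:

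- Month 3: 84/7 = 12
- Month 6: 175/7 = 25
- Month 12: 357/7 = 51

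Share after the sample = 1 − (p + b)/(p + T). For example, for a treatment-naive patient at Month 3, 1 − 12/52 = 0.769 and 1 − 12/104 = 0.885.

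| Group | Month 3, T = 52 / 104 | Month 6, T = 52 / 104 | Month 12, T = 52 / 104 |
|---|---|---|---|
| Treatment-naive | 0.769 / 0.885 | 0.519 / 0.760 | 0.019 / 0.510 |
| CS16-volanesorsen | 0.513 / 0.708 | 0.346 / 0.608 | 0.013 / 0.408 |
| CS6-volanesorsen | 0.385 / 0.590 | 0.260 / 0.506 | 0.010 / 0.340 |

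Pooling adds to this. A treatment-naive patient who completes the extension has 104 injections. So does a CS6-volanesorsen patient who stops at Week 52 (52 + 52). They share one position on the axis, but by Month 3 they had received 12 and 12 + 52 = 64 injections.

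**2. Correlation with no dose effect**

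This simulation is illustrative; apart from N = 70 and the 52- and 104-week totals, its inputs are assumptions and not figures from the SAP.

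*Lipids.* Month 3 percent change has mean −50 and SD 25. Patients who stop early have 14 to 51 injections in total; the others have 52 or 104 in equal proportions. The mean r with total injections is:

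- 0.00 if stopping is unrelated to response;
- −0.15 if the log-odds of stopping rise by 0.5 per SD of poorer response;
- −0.28 if they rise by 1 per SD.

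A negative r looks like a larger reduction with more drug. With N = 70, the standard error of atanh(r) is 1/√67 = 0.122. The last two values are then 0.151/0.122 = 1.2 and 0.288/0.122 = 2.4 standard errors from zero.

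*Platelet nadir.* The mean r with total injections is −0.12 with no stopping rule, because longer observation gives more chances of a low value. It is +0.16 or +0.39 if treatment ends at an assumed count below 50 or 75 thousand. Between 44% and 49% of injections come after the nadir.

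**The case against.** The best reply is that Section 3.3.4 is silent on a cut-off and does not rule one out. A programmer could count only up to the plotted assessment. That reading would remove the timing problem, but nothing in the section directs it: the stated rule is a total over both studies. The equal counting of part doses is explicit, and so is the pooling.

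A second reply is that Section 3.3 already plans a table and listing by three-month window, with dose level, TG and platelet nadir side by side. That is useful, time-aligned information. It covers TG only among the nine lipid measures, and it does not change the correlation in Section 3.3.4.

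Some stronger readings are tempting, and the SAP does not support them:

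- *Most of the axis is always post-outcome drug.* The 88% needs a Month 3 value, a treatment-naive patient and a complete extension. At Month 12, for patients who stop at Week 52, the share is 1% to 2%.
- *The count ignores dosing changes altogether.* Biweekly dosing and missed doses do lower it. Only the amount per injection is lost, and the SAP gives no frequency for that.
- *The plots can show nothing.* They can be drawn and described; what fails is reading them as a dose association.
- *Low platelets make the nadir plot run in a known wrong direction.* Stopping for low counts and longer observation pull in opposite directions. The net sign depends on thresholds that the SAP leaves to the protocol.
- *Pearson's coefficient is wrong because percent change is skewed.* The SAP gives no distribution for any of the nine measures, so this would be a preference.

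**Conclusion.** The point stands, mainly for the lipid plots. Section 3.3.4 states an exposure rule that does not measure what the section sets out to examine. The post-outcome shares rest on full weekly dosing and on Months 3, 6 and 12 being the values plotted, which the section does not say. They are large at Months 3 and 6, and at Month 12 only for patients who go on into the extension. The simulated correlations show that a spurious association is possible; they do not estimate its size in this trial.

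The importance is low. Section 1.3 declares no formal hypothesis and makes efficacy testing exploratory, and no main conclusion depends on these plots. For the platelet plot, the conclusion is limited to how it may be read: low platelets can end or reduce dosing, while longer treatment gives more chances of a low value.

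**What to change.** In Section 3.3.4:

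1. Name the lipid time point, for example Months 3, 6 and 12, with one plot for each.
2. Replace the injection count with cumulative mg of volanesorsen actually received up to that assessment, including index-study volanesorsen where the index baseline is used.
3. Show or compute the correlation separately for treatment-naive and previously treated patients.

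In Section 3.5.4.2, state that the plot of platelet nadir against total injections is descriptive and cannot be read as a dose effect. Capping the count at the nadir date is not a clean remedy, because a later nadir automatically has more injections before it.

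The cost is minor programming. Section 3.3 already uses dose level by window and Section 3.4.1.2 uses actual dose, so no new data collection is indicated. One limit remains: at a fixed time point within a group, differences in cumulative mg arise from missed or adjusted doses, which may themselves follow tolerability. The revised plots should therefore still be labelled exploratory.

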3.3.5 Frequency and severity of patient reported abdominal pain

The maximum intensity of abdominal pain related to disease will be collected on the FCS symptom questionnaire and reported by patients weekly on Bracket electronic patient reported outcomes (ePRO). The average maximum intensity of patient reported abdominal pain score during the on-treatment period will be summarized. The patients' reported results will be mapped to each visit week based on the visit window specified in [section 3.2.1](#). If patients have multiple results within a visit window, the worst score will be used for summary and analysis. The results at Week 1 will not be included in the on-treatment period, since the results are reported retrospectively to collect the symptoms of patients during the past week. The missing data will be imputed by using Next Observation Carried Back (NOCB) if there is a subsequent score available. Otherwise, the missing data after the last available score of each patient will not be imputed.

Two (2) types of summary tables will be provided in the subset of FAS patients who reported any abdominal pain (pain score > 0) during the screening period and Week 1. Baselines are defined in the [section 3.2.3](#).

1. Change from both **Index Study Baseline** and **Open-label Study Baseline** in the average of maximum intensity of patient reported abdominal pain will be summarized.
2. Change from both **Index Study Baseline** and **Open-label Study Baseline** in the worst weekly patient reported maximum intensity abdominal pain score during the treatment period will be summarized.
3. The same method described above will be used to impute the missing data in exploratory analyses.

The abdominal pain score in each week will be categorized to no pain (pain score: 0), mild (pain score: 1–3), moderate (pain score: 4–6), or severe (pain score: 7–10). A summary by the category will also be provided for safety set overall, and for CS6 subjects who roll-over to CS7. Other information of the abdominal pain questionnaires will be listed in a patient data listing.

Summary table and figure for abdominal pain intensity change for patients with pain at baseline in CS6 subjects who roll-over to CS7 will be generated.

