2 PROCEDURES

The study for an individual patient will generally consist of the following periods:

- Screening/Qualification:
- Qualification of Group 1 and 2 patients (participated in ISIS 304801-CS6 or ISIS 304801-CS16 index study): A qualification period of up to 2 weeks (unless approved by the Sponsor).
- Screening and Qualification of Group 3 patients (did not participate in an index study): An up to 8-week screening and qualification period, including a diet stabilization period of at least 6 weeks.
- A 52-week treatment period during which volanesorsen will be administered as a once weekly SC injection
- Option to participate in an extended treatment period (up to an additional 52 weeks)
- A 13-week post-treatment evaluation period

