	104	722	674 to 743
	117	813	744 to 858
	130 (France)	904	859 to 949
Abdominal Pain			
	m	$n \times 7 + 1$	$mx7+3 \text{ to } mx7-3,$ $m = -1, -2, \dots$
	...		
	-2	-13	-11 to -17
	-1	-6	-4 to -10
	1	1	1 to -3
	2	8	5 to 11

	3	15	12 to 18
	n	(n-1) × 7+1	(n-1) × 7-2 to (n-1) × 7+4
	...		
MRI			
	Screening	NA	≤ 14
	52	358	298 to 418
Quality of Life Assessments (EQ-5D, SF-36)			
	1	1	1
	13	85	55 to 115
	26	176	146 to 206
	52	358	328 to 404
	65	449	405 to 479
	78 (France)	540	496 to 570
	117 (France)	813	769 to 843
	130 (France)	904	860 to 934

Note: Regarding lipid measurements for efficacy analyses, mapped observed assessments defined in this table will be derived further. The derivations for baselines are described in [section 3.2.3](#). The derivations for Month 3, 6 and 12 are described in [section 3.3.1](#).

Non-efficacy by visit assessments will be summarized using the visit labels provided in the data. Multiple results with the same visit label will be averaged.

Unscheduled results and data from local labs will not be included in the by visit summaries but will be used in the determination of baseline, in the laboratory abnormality, stopping rule, and platelets reduction analyses presented in data listings.

Unscheduled results from the central lab will be used in the determination of baseline, laboratory abnormality summaries, and shift from **safety baseline** to worst post-baseline, and platelets reduction analyses only, and presented in data listings. Local lab data will be only used in platelet analyses (including by visit summaries, abnormality summary, shift from Baseline to worst post-baseline, reduction analyses), and presented in data listings.

Summary tables and figures will NOT be presented by the treatment group in each index study (ISIS 304801-CS6 or ISIS 304801-CS16) and the newly enrolled patients as a separate group per protocol. Per Sponsor decision, most summary tables and figures will be presented in the following groups, i.e. Treatment naive group, CS6-Volanesorsen, CS16-Volanesorsen, and Overall, if applicable.

Note: “Treatment naive group” for most tables and figures is a combined group of subjects including CS7-New, CS6-Placebo and CS16-Placebo. When the summary is based on **Index Study Baseline**, “Treatment naive group” is a combined group of subjects including CS6-Placebo and CS16-Placebo.

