3.2.3 Baselines and Other Definition

Baselines for fasting lipid measurement:

Definitions of baselines, including the **Index Study Baseline** (for Group 1 and Group 2 only) and the **Open-label Study Baseline** (for Group 1, 2, and 3), are given below for the purposes of the final analysis.

- **Index Study Baseline for Group 1 and 2** is defined as the average of Index Study Day 1 pre-dose assessment and the last measurement prior to Index Study Day 1 pre-dose assessment. If one of the two measurements is missing, then the other measurement will be assigned as the baseline value. If both are missing, then the baseline will be set as missing.
- **Open-label Study Baseline for Group 1, 2 and 3** is defined as the average of open-label Day 1 pre-dose assessment and the last measurement prior to open-label Day 1. If one of the two measurements is missing, then the other measurement will be assigned as the baseline value. If both are missing, then the baseline will be set as missing.

Baselines for QOL (EQ-5D, SF-36):

1. **Index Study Baseline for Group 1** is defined as the last non-missing assessment on Week 1 of treatment, volanesorsen or Placebo, in index studies.
2. **Open-label Study Baseline for Group 1, 2 and 3** is defined as the last non-missing assessment on Week 1 in this Open-label study.

Baselines for patient reported abdominal pain:

1. The average of maximum intensity:
2. **Index Study Baseline for Group 1** is defined as the average of maximum intensity during the screening period and Week 1 in index studies.
3. **Open-label Study Baseline for Group 1, 2 and 3** is defined as the average of maximum intensity within 4 weeks (including week 1) prior to Day 1 of treatment in this open-label study.
4. The worst of maximum intensity:
5. **Index Study Baseline for Group 1** is defined as the worst of maximum intensity during the screening period and Week 1 in index studies.
6. **Open-label Study Baseline for Group 1, 2 and 3** is defined as the worst of maximum intensity within 4 weeks (including week 1) prior to Day 1 of treatment in this open-label study.

Safety Baseline for Platelet count: is defined as the average of all available measurements, including central lab measurements and local lab measurements, prior to Day 1 of volanesorsen, i.e.

1. For subjects in Group 1 and 2 who were treated with volanesorsen in the index study, it is all available measurements prior to Day 1 of treatment in index study

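### Abdominal-pain change is tabulated only in patients with pain at entry, so the average score tends to fall with no drug effect; the selection weeks and the worst-score windows are also not aligned with the open-label baseline

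*SAP*

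**What the plan says.** SAP section 3.3.5 plans two change tables, one for the average and one for the worst weekly score, both "in the subset of FAS patients who reported any abdominal pain (pain score > 0) during the screening period and Week 1". The second reports change "in the worst weekly patient reported maximum intensity abdominal pain score during the treatment period will be summarized". The additional change table and figure for CS6 roll-overs is likewise confined to patients with pain at baseline.

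Section 3.2.3 fixes the baselines. The average open-label baseline "is defined as the average of maximum intensity within 4 weeks (including week 1) prior to Day 1 of treatment in this open-label study", and the worst-score version "is defined as the worst of maximum intensity within 4 weeks (including week 1) prior to Day 1 of treatment in this open-label study". The Group 1 index baseline "is defined as the average of maximum intensity during the screening period and Week 1 in index studies".

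Section 2 gives the CS7 run-in. For Groups 1 and 2 it is "A qualification period of up to 2 weeks (unless approved by the Sponsor"; for Group 3 it is "An up to 8-week screening and qualification period, including a diet stabilization period of at least 6 weeks". In section 3.2.1 the Treatment naive column "is a combined group of subjects including CS7-New, CS6-Placebo and CS16-Placebo".

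Pain outputs without selection on pain exist, but they show level or rate and not change:
- the on-treatment average and the pain categories (3.3.5);
- the 3-month window table (3.3);
- the yearly rate of moderate or severe pain (3.3.9).

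**The concern.** Every planned change-from-baseline result for pain depends on the patient having had pain at entry, and CS7 has no concurrent control. A patient caught in a bad spell tends to look better later whatever the treatment does. A negative mean change in the subset would therefore be easy to misread as efficacy.

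Two further points affect how the tables can be built and read. The weeks that decide entry to the subset are not the weeks that form the open-label baseline, and section 3.3.5 does not say which study's screening period is meant. The worst-score table also compares maxima taken over very different lengths of time.

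**Working it through.** The SAP states no expected pain change, so there is no figure to reproduce. The check asks what the tables would show if the drug did nothing.

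**Inputs from the SAP**
- Open-label baseline: B = 4 weekly scores (Weeks 1, -1, -2, -3), section 3.2.3.
- Weekly windows, section 3.2.1: Week -2 is days -11 to -17; the general formula puts Week -8 at days -53 to -59. Counting Week 1, the run-in gives up to W = 3 scores in Groups 1 and 2 and up to W = 9 in Group 3.
- Treatment: 52 weeks (section 2). Week 1 is not counted as on-treatment (section 3.3.5), which leaves 51 scores.

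**Assumptions, not in the SAP**
- Each patient has a weekly pain probability p from a beta distribution with mean μ = 0.05 to 0.40 and intraclass correlation ρ = 0.1 to 0.6.
- Mean score is 4 when pain is present.
- Weeks are independent given p.

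**Step 1: average score.** Let P = 1 - E[(1-p)^W] be the share selected and e = E[p(1-p)^W]. The expected change is -4 × min(W/B, 1) × e/P. For W ≥ B this is e/μ as a fraction of baseline.

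Example with μ = 0.2, ρ = 0.3, W = B = 4: P = 0.440 and e = 0.0413. Baseline is 4 × 0.2/0.440 = 1.82; on treatment it is 4 × (0.2 - 0.0413)/0.440 = 1.44. The change is -0.38, or 0.0413/0.2 = 21%.

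| Selection window | Change, all settings | Fall, % of baseline | μ = 0.2, ρ = 0.3 |
|---|---|---|---|
| 3 scores (Groups 1 and 2) | -0.18 to -0.75 | 6-59% | -0.42 (22%) |
| 4 scores (matched) | -0.17 to -0.71 | 6-58% | -0.38 (21%) |
| 9 scores (Group 3) | -0.04 to -0.25 | 2-36% | -0.12 (9%) |
| No selection (all FAS) | -0.004 to +0.007 (simulated) | about 0 | 0.00 |

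For identical patients with p = 0.2, the matched figure is 0.8^4 = 41%. With p from Beta(1,4), also mean 0.2, it is (4×5×6×7)/(6×7×8×9) = 840/3024 = 28%.

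**Step 2: mismatch with the open-label baseline,** reading the selection window as the CS7 run-in, with the same p for everyone.
- Selected Group 3 patients whose baseline is 0: (1-p)^4 × [1-(1-p)^5] / [1-(1-p)^9]. At p = 0.1: 0.656 × 0.410/0.613 = 44%. At p = 0.2: 0.410 × 0.672/0.866 = 32%.
- Roll-overs with baseline pain who are left out: p(1-p)^3 / [1-(1-p)^4]. At p = 0.1: 0.0729/0.344 = 21%. At p = 0.2: 0.1024/0.590 = 17%.

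Between-patient differences shrink both shares. From the selected shares P, they are (P9 - P4)/P9 and (P4 - P3)/P4. At μ = 0.2, ρ = 0.3 these give (0.584 - 0.440)/0.584 = 25% and (0.440 - 0.386)/0.440 = 12%.

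**Step 3: worst score** (simulation, 40,000 patients per setting, open-label baseline). The maximum over 51 weeks minus the maximum over 4 weeks, with no drug effect, is:
- +1.0 to +2.1 points with 3- or 4-score selection;
- +2.3 to +3.1 points with 9-score selection;
- +0.5 to +3.5 points in all FAS patients.

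For selected patients with only 12 on-treatment scores it runs from -1.0 to +1.5.

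**The case against.** The study has no primary efficacy endpoint and no formal hypothesis, and it is to be evaluated by summary tables. Showing change in symptomatic patients is common, because a patient at 0 cannot improve. Level and rate summaries without pain selection limit reliance on the subset. An all-FAS change would not be a clean drug effect either: the study is uncontrolled, and roll-overs from the volanesorsen arms are already treated at the open-label baseline. All of this stands, and it limits the weight of the point. It does not remove it: a descriptive mean that is negative under no effect still misleads, and no unselected change is planned to set beside it.

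Four stronger readings are tempting but are not supported:
- *The window mismatch causes the fall.* It does not. The fall appears with exactly matched windows, and the longer Group 3 window weakens it.
- *Both tables show a spurious fall.* Only the average does so in every setting. Over full follow-up the worst score is pushed upward, and dropping the selection does not cure that.
- *The mismatch affects every table.* The Group 1 index baseline carries the same wording as the selection rule.
- *Roll-overs are certainly confined to two weeks.* Section 3.3.5 does not name the study. Groups 1 and 2 have a qualification period rather than one called screening, so the defect is an undefined window.

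**Conclusion.** The point holds in three parts.

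1. The average-score change tables are open to regression to the mean. The fall with no drug effect is about 6-58% of baseline with matched 4-week windows, against about 0 in all FAS patients. The direction was the same in every setting tried. The size rests on assumed pain frequency, between-patient correlation and independence between weeks; 41% is the case of identical patients and should not be taken as the expected size.
2. For the open-label baseline, the subset is undefined and its weeks do not match. On the CS7 run-in reading, with pain in 10-20% of independent weeks, about 32-44% of selected Group 3 patients would have baseline 0 and about 17-21% of roll-overs with baseline pain would be left out. These shares are lower if patients differ. The Treatment naive column pools both kinds of patient. This alters the size of the artefact and the make-up of the groups; it does not create the artefact.
3. Over full follow-up, the worst-score comparison with the open-label baseline is biased upward, with or without the selection.

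A reader might infer that pain is the leading endpoint or that a formal conclusion is at risk. The SAP lists it among several efficacy endpoints without ranking and plans no formal hypothesis, so what is at stake is the reading of descriptive tables.

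**What to change.** In section 3.3.5:
- Add change tables for the average score in all FAS patients with a baseline pain score.
- Keep the pain-at-baseline subset, but name the study and define the subset on exactly the weeks of the baseline being analysed (Index or Open-label), the same for all groups. Label its results as subject to regression to the mean.
- Compare worst scores over windows of equal length, for example the worst in each 4-week block against the 4-week baseline. This removes the length artefact; the regression label still applies in the subset.
- For CS6 roll-overs with index-baseline pain, show the CS6-Placebo course during the index study beside the change, as the course without drug.

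The cost is SAP wording and a few extra tables from data already collected. The mean change in all FAS patients will be smaller because many may score 0, and the text should say so.
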